## CONFIDENTIAL

DE Cohort	Screening a	Cycle (Induction Period)			Follov (post-fina adminis	v-Up al dose stered)	
Study Procedure		Intervention Period (In-Patient)		Observation Period (Outpatient)	TDV⁵	Follow- Up	Notes
Week	≤4	1	- 2	3 - 4	+4		
Day	≤28	-1	1 - 13	14 - 28	+30d		
							sample, Days 8 - 12 – at EOI+6hrs: Day 13 – single sample prior to discharge. Clinical chemistry including uric acid and phosphate will be measured at least every 6 hours for the first 48 hours following initiation of daily dosing period, then at least twice daily up to an including Day 5 dosing of each daily dosing period, and more frequently as clinically indicated. Clinical chemistry samples should be collected more frequently if clinically indicated (such as cases of TLS). A sample will also be taken between Day 20 and Day 22 during the outpatient period of the cycle. See Section 10.2 for complete list of required laboratory assessments.
C-Reactive Protein	x		Х	Х	х		Sample collection times: Day 1 at predose, EOI+8h and +24h for first dose, then pre dose at Day 5 and Day 12 of each cycle.
Thyroid function c	X		Х		x		Sample collection times: Day 1 at predose of Cycles 1 and 3.
Troponin I and T	х		Х		Х		See Section 6.4.1.5 for management of cardiac events. Samples will be collected on Day 13.
BNP (or NTproNBNP)	Х	Repeat as clinically indicated					Repeat test as outlined in management of cardiac events (Section 6.4.1.5)
eGFR	Х						See Section 7.1.2 for management of renal events (if needed).

# CONFIDENTIAL

DE Cohort	Screeningª	Cycle (Induction Period)			Follov (post-fin adminis	w-Up al dose stered)	
Study Procedure		Intervent (In-P	tion Period atient)	Observation Period (Outpatient)	TDV⁵	Follow- Up	Notes
Week	≤4	1	- 2	3 - 4	+4		
Day	≤28	-1	1 - 13	14 - 28	+30d		
Urinalysis⁰	x		Х		Х		Sample collection times: Days 1, 8 and 13 of each cycle. If urinalysis is abnormal, a microscopy should be performed.
Coagulation	x		х				Sample collection times: at screening and prior to administration of first dose of GSK3745417 and at Day 8 of each cycle. Additional coagulation samples should be collected in the event of CRS (see Section 6.4.1.4)
Study Intervention	•						· · ·
Administer GSK3745417			X				GSK3745417 will be administered the same dose within each cycle on Days 1 – 5 and Days 8 - 12 QD. Participants will receive up to 3 cycles of treatment before moving to Q1W or Q3W dosing (Section 6.1). See Section 4.1 for maximum duration of study intervention. See Section 4.1 for safety and tolerability parameters to be reviewed prior to each daily dose
Non-Azole Antifungal		х	Х	Х			Non-azole antifungals should be administered if indicated, per local standard, on Day -1 through Day 28 of each cycle.
Tumor Lysis Syndrome Prophylaxis		x					All participants should receive tumor lysis syndrome (TLS) prophylaxis prior to date of first dose of each cycle on Day -1 according to institutional guidelines (e.g., participants should receive IV fluids ± allopurinol and consider alkalization of urine and

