# Figure 1 Part 1 Induction Intra-patient Dose-Escalation Study

\* Patients in C3 dose level in all cohorts will be continuing dosing Q1W at C3 dose level

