# Figure 2 Part 1: Dosing and Observation Timeline for Each Cycle

# Figure 3 Part 2: Expansion Study: Induction and Maintenance Dose Escalation

# 1.3. Schedule of Activities (SoA)

- The schedule of activities for each Part of the study may be found on the following pages. For all parts, the following apply:
- The timing of planned study assessments may change during the study based on emerging data/in-stream data review to ensure appropriate monitoring.
- Any changes in the timing of time points for any planned study assessments as the result of emerging pharmacokinetic/pharmacodynamic data from this study must be documented and approved by the relevant study team member and then archived in the sponsor and site study files but will not constitute a protocol amendment.

- The Competent Authority (CA) and ethics committee (EC) will be informed of any safety issues that constitute a substantial amendment and require alteration of the safety monitoring scheme or amendment of the informed consent form (ICF). The changes will be approved by the CA and the EC before implementation.
- For Part 1, Table 1 applies to Cycles 1, 2, and 3 in the Dose Escalation Cohort After completing the assessments in Cycle 3, participants would proceed to complete the assessments in Table 3 for the maintenance phase.
- For Part 2, after completing the assessments in Table 2, participants would proceed to complete the assessments in either Table 3 or Table 4 for the maintenance phase.

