# 1.3.5. Part 2 – GSK3745417 Maintenance Every 3 Weeks

### Table 4 Schedule of Activities (GSK3745417 Maintenance Every 3 Weeks- Part 2 only)

Q3W Cohort	Stu	dy Maintenance Period			
Study Procedure	G: V	SK417 Every 3 Veeks (Q3W)	TDV⁵	Follow-Up (post- final dose administered	Notes
Week		1 and Thereafter a	+4	Q4W	
Day	-1	1 and Thereafter	+30d		
Safety Assessments					
In-House Monitoring	х	Q3W			Participants should be monitored in a medically qualified unit/clinic/hospital starting on Day -1 and 24 hours following the administration of GSK3745417 on Day 1. This requirement may be eliminated as safety data emerge.
Physical Exam		Q3W	х		Brief or targeted physical exams will be performed on Day 1 at predose (within 1h prior to dosing), and as clinically indicated. Refer to Section 8.2.1 for physical examination details.
ECOG PS		Q3W	Х		
Vital Signs	х	Q3W	х		Vital signs should be collected at least 6 times on Day -1 within 24 hours prior to dosing and on Day 1 at predose (within 1 hour prior to dosing) and at EOI+30m, +1h, +2h, +4h, +6h, +8h, +12h and +24h.
Weight		Q3W	Х		
Echocardiogram		Week 1, then Q9W	x		If available, a 3D ECHO is preferred, otherwise a 2D ECHO may be performed. Where the quality of the ECHO examination is sub-optimal, MUGA scans may be used. The modality used at baseline should be repeated throughout the study to ensure comparison to baseline. At TDV, ECHO/MUGA does not need to be performed if an on-study ECHO has been conducted within the 4 weeks prior to visit.

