# 4. STUDY DESIGN

# 4.1. Overall Design

This is a Phase 1 open-label study of intravenous GSK3745417 to evaluate safety, tolerability, pharmacokinetics, pharmacodynamics and determine RP2D and schedule in participants with relapsed or refractory acute myeloid leukemia (AML) and high-risk myelodysplastic syndrome (HR-MDS).

The study will be conducted in a staged approach consisting of 2 parts. Part 1 represents dose escalation to determine a cohort level MTD and incorporates intra-patient dose escalation within cohorts to minimize the potential for a participant to be exposed to a non-efficacious sub-therapeutic dose. Dosing in Part 1 will include 3 initial cycles followed by "maintenance" at a weekly dosing schedule. Part 2 represents an expansion cohort at the recommended induction dose/doses and schedule from Part 1 for 3 cycles, followed by either a weekly, every 3 weeks, or less frequent dosing schedule for "maintenance." Approximately 72 participants will be enrolled: approximately 22 participants in Part 1 and 50 participants in Part 2.

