### Part 1

Part 1 will evaluate a dosing schedule of a 5 days on/2 days off schedule for 2 weeks, and then have an additional 2 weeks off dose for observation for a total of 28 days in each cycle (5/2/5 q28d). Once an MTD has been established, additional cohorts may be opened to refine dosing frequency optimization. Each cohort will include at least

3 participants. Part 1 will include intra-patient dose escalation for 3 cycles, according to safety and tolerability parameters. The starting dose for Cycle 1 will be escalated in the next dose escalation cohort until a cohort level MTD is reached. The first participant at the starting dose level(s) of each cohort will begin treatment after review of safety data and DEM to allow assessment of initial safety data before beginning the next participant's treatment. The dosing of subsequent participants will be staggered by  $\geq 5$  days.

Day	-1	1	2	3	4	5	6	7	8	9	10	11	12	13	14-28
GSK3745417		Х	Х	Х	Х	Х			Х	Х	Х	Х	Х		
In-patient	Х	Х	Х	Х	Х	Х	Х	Х	Х	Х	Х	Х	Х	Х	
Non-azole antifungal	Х	Х	Х	Х	Х	Х	Х	Х	Х	Х	Х	Х	Х	Х	Х

Table 6	Dosing and Hospitalization Schedule for Cycles 1 - 3

Dose escalation will initiate with Cycle 1 at 12.5 µg GSK3745417 as the first cohort and the Cycle 1 dose will increase by 2-fold between cycles (3 dose levels). The starting dose of subsequent cohorts will increase by 2-fold from Cycle 1 of the previous cohort. Patients may be dose reduced for subsequent cycles if there is lack of tolerability in the previous cycle (Section 6.4). The DLT period will be 28 days starting at Day 1 of Cycle 1 of each cohort. After 3 induction cycles, if a CR or PR (IWG) is observed (See Appendix 9), each patient will continue with maintenance weekly dosing at the Cycle 3 dose level until disease progression or unacceptable toxicity. Participants with progressive disease after 3 induction cycles will be withdrawn from study. Participants with stable disease or PR after 3 cycles might receive additional cycles if the assessment by the investigator determined a benefit and GSK Medical Monitor agrees.

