# 6.1. Study Intervention(s) Administered

GSK3745417 will be administered to participants at each study site under medical supervision of an investigator or designee. Cytokine-related AEs including changes in vital signs may begin within several hours of administration of GSK3745417. Participants must be monitored in the clinic/hospital throughout dosing in the initial cycles and for up to 24 hours after administration of the Q1W or Q3W maintenance doses, or longer as clinically indicated. Guidelines for monitoring cytokine-related AEs and tumor lysis syndrome are summarized in Section 6.4.

For Part 1, the dosing schedule each Cycle from 1 - 3 is 5 days on / 2 days off / 5 days on followed by observation for 2 weeks. After 3 cycles, participants will move to a dosing schedule of once every week (Q1W). For Part 2, after the induction regimen determined from Part 1, participants will enter a maintenance phase at a dose and schedule determined by emerging FIH data.

The specific time of study treatment administration (e.g., time of the week for first administration; time of the day for each administration) should take into consideration PK sampling time points and study visit procedures and will be recorded in the source documents and in the eCRF.

ARM NameInterventionIntervention NameGSK3745417TypeDrugDose FormulationTo be provided in the study reference manualDosage FormPowder for Solution for InjectionUnit Dose Strength(s)2 mg/vial

Weekly dosing may be done  $\pm 24$  hours and Q3W dosing may be done  $\pm 72$  hours.

Dosage Level(s)	12.5 µg – 800 µg (to be determined)		
Route of Administration	IV injection through a central or PICC line		
Use	experimental		
IMP and NIMP	GSK3745417		
Sourcing	Provided centrally by the Sponsor		
Packaging and Labeling	Study Intervention will be provided as 1 vial in a carton. Each vial and carton will be labeled as required per country requirement.		
Current/Former Name(s) or Alias(es)	N/A		

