### 4.5.1. Extent of Exposure

Exposure to GSK3745417 will be summarized according to cumulative actual dose, number of cycles, time on study treatment (weeks) with separate sections for induction dosing and maintenance dosing in one table. Descriptive statistics including mean, median, standard deviation, minimum, and maximum will be calculated.

The cumulative dose, converted to and displayed in mg, is the sum of the actual dose administered in micrograms during each infusion for a subject throughout the study. For induction dosing, cumulative dose will be summarized by cycle. For induction cycles, the number of cycles will be calculated by the number of GSK3745417 doses received during the induction phase divided by 10. For subsequent maintenance cycles, the number cycles will be calculated by (last maintenance infusion date – first maintenance infusion date + 7)/28.

Subject level details for extent of exposure to study treatment will be listed. The listing will include cycle, total dose taken per cycle, cycle day, start and stop dates, scheduled dose, actual dose, and cumulative dose. Exposure data will be listed in both units (mg and  $\mu$ g).

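### Table 1 lets Part 1 participants move to weekly or three-weekly maintenance, while the section it cites and the rest of the plan give weekly only; the passages must be reconciled

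*Protocol*

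**What the plan says.** The dosing row of Table 1 (Protocol Section 1.3.1), which is the Part 1 schedule of activities, reads: "Participants will receive up to 3 cycles of treatment before moving to Q1W or Q3W dosing (Section 6.1". The other passages on Part 1 maintenance give one schedule:

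- **Protocol Section 6.1**, the section that Table 1 cites: "After 3 cycles, participants will move to a dosing schedule of once every week (Q1W".
- **Protocol Section 4.1, Part 1**, and in the same terms Section 1.1: "each patient will continue with maintenance weekly dosing at the Cycle 3 dose level until disease progression or unacceptable toxicity".
- **Footnote to Figure 1** (Section 1.2), repeated in Section 4.1: "Patients in C3 dose level in all cohorts will be continuing dosing Q1W at C3 dose level".
- **Introduction to Section 1.3**, on Part 1: "After completing the assessments in Cycle 3, participants would proceed to complete the assessments in Table 3 for the maintenance phase". Table 3 is the weekly table.
- **Title of Table 4** (Section 1.3.5), the every-3-weeks table: "Schedule of Activities (GSK3745417 Maintenance Every 3 Weeks- Part 2 only".
- **SAP Section 1.2** describes Part 1 maintenance as weekly at the Cycle 3 dose level.

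SAP Section 4.5.1 counts maintenance cycles from the first and last maintenance infusion dates. It adds a fixed 7 days and divides by 28; the expression ends "first maintenance infusion date + 7)/28".

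**The concern.** The Table 1 note stands in the row that tells a site what to give, so it works as a dosing instruction. It names a schedule that its own cross-reference does not give for Part 1. A site acting on it would have no schedule of activities to follow, because the only every-3-weeks table is assigned to Part 2. The two maintenance tables also differ in substance:

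| Item | Table 3 (weekly) | Table 4 (every 3 weeks) |
|---|---|---|
| Dosing window | ±1 day | ±3 days |
| Troponin | every 2 weeks | every 3 weeks |
| Echocardiogram after Week 1 | every 8 weeks | every 9 weeks |
| Full PK profile | Week 3 | Week 7 |

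The statistical side comes second. SAP Section 1 limits the report to Part 1, so the maintenance exposure reported will be Part 1 exposure, and its cycle count has a 7-day interval built in.

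**Working it through.** **1. Does the cross-reference settle the schedule?** Table 1 offers two schedules and points to Section 6.1. That section's Part 1 sentence gives one, weekly. Its general monitoring paragraph mentions both maintenance schedules, but it covers both parts of the study. Section 1.3 sends Part 1 to Table 3 and offers Part 2 a choice of Table 3 or Table 4. Among the passages on the Part 1 schedule, the Table 1 note alone names every-3-weeks dosing.

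**2. Would the weekly table serve a participant dosed every 3 weeks?** Doses would fall on Days 1, 22 and 43, that is in Weeks 1, 4 and 7. Table 3 puts its full PK profile in Week 3, timed from that week's injection. No dose would be given that week, so the predose and post-injection samples would have nothing to be timed from. Table 4 uses Week 7, which is a dosing week.

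**3. Dose intensity at the same dose per infusion.**

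- Weekly: 28/7 = 4 doses per 28 days.
- Every 3 weeks: 28/21 = 1.33 doses per 28 days.
- Ratio: 4/1.33 = 3. Over 12 weeks this is 12 doses against 4.

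**4. The SAP cycle formula.** For n doses given every d days, last minus first infusion date is d(n − 1). The SAP value is [d(n − 1) + 7]/28. The time covered, in 28-day cycles, is dn/28. The shortfall is therefore (d − 7)/28, whatever n is.

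- Weekly, d = 7: shortfall 0. Twelve doses give (77 + 7)/28 = 3.0 cycles, which is exact.
- Every 3 weeks, d = 21: shortfall 14/28 = 0.5 cycle. Four doses give (63 + 7)/28 = 2.5 cycles, against 84/28 = 3.0.

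| Time covered | Cycles covered | SAP formula, weekly | SAP formula, every 3 weeks | Shortfall, every 3 weeks |
|---|---|---|---|---|
| 3 weeks | 0.75 | 0.75 | 0.25 | 0.5 (67%) |
| 12 weeks | 3.0 | 3.0 | 2.5 | 0.5 (17%) |
| 24 weeks | 6.0 | 6.0 | 5.5 | 0.5 (8%) |
| 48 weeks | 12.0 | 12.0 | 11.5 | 0.5 (4%) |

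Adding the planned interval d in place of 7 gives [d(n − 1) + d]/28 = dn/28. That leaves the weekly results unchanged and removes the shortfall at any other interval.

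**The case against.** The strongest reply is that the plan all but answers the question itself. A site that follows the cross-reference reaches weekly dosing, the routing in Section 1.3 sends it to the weekly table, and the figure footnote covers all cohorts. Table 2, for Part 2, has nearly the same sentence, so the phrase may have been carried across from there. Part 1 had also finished recruiting when the study was terminated (SAP Section 4.8). All of this bears on how likely harm is. None of it removes a conflicting instruction from a dosing row, and the documents cannot show that the wording was carried over.

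The reply is right about several stronger readings that a reader might infer:

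- **That the SAP formula is wrong.** SAP Section 1.2 describes weekly maintenance, and for weekly dosing the formula is exact.
- **That the exposure table would understate weeks on treatment or dose.** SAP Section 4.5.1 lists cumulative dose, number of cycles and weeks on treatment as separate measures. The formula defines only the number of maintenance cycles. Cumulative dose is summed from doses given, and no formula is stated for weeks.
- **That safety and PK results would be pooled under one maintenance heading.** SAP Sections 4.1.1 and 4.3.1.2 present adverse events by dose level, and PK by dose level and visit or day. Only the exposure table has a maintenance section. Those outputs are not split by dosing interval either, but that matters only if two intervals were used.
- **That the protocol rules out any other interval in Part 1.** Section 6.4.1 leaves room for alternative schedules for a participant or cohort, and Section 4.1 for additional cohorts to refine dosing frequency.

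**Conclusion.** The inconsistency is real, and it is confined to one phrase in Table 1. It bears on dosing and on which monitoring schedule applies, so it should be reconciled. The primary Part 1 objective concerns daily induction dosing and is not touched.

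The three-fold difference in dose intensity assumes the same dose per infusion; the documents fix the Part 1 maintenance dose, at the Cycle 3 level, only for weekly dosing. The 0.5-cycle shortfall assumes doses given exactly on the planned interval, and it applies only to a participant dosed every 3 weeks. The documents do not report whether there was one.

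Few people could be affected. Sections 1.1 and 4.1 tie maintenance to a complete or partial response after three induction cycles, among about 22 participants. The documents give no Part 1 response rate. Purely as an assumption, the Part 2 design rates of 10% and 30% would give 0.10 × 22 = 2.2 and 0.30 × 22 = 6.6, roughly 2 to 7 people.

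**What to change.** 1. **Protocol.** Reconcile the dosing note in Table 1 with Sections 1.1, 4.1 and 6.1, the Figure 1 footnote, the routing in Section 1.3, the title of Table 4 and SAP Section 1.2. This review takes no position on which schedule is right. If every-3-weeks dosing was meant to be possible in Part 1, the routing and the scope of Table 4 need to say so. Cost: one line, or a few if the scope of Table 4 changes. With recruitment finished, a clarification in the clinical study report may serve as well as an amendment.
2. **Data check.** State in the report which maintenance interval each Part 1 participant was given. The subject-level exposure listing in SAP Section 4.5.1 already carries dosing dates.
3. **SAP, only if needed.** If any Part 1 participant was dosed at an interval other than weekly, through the reconciliation or through the flexibility in Sections 4.1 or 6.4.1, replace the fixed 7 days in the cycle formula with that participant's planned interval. Cost: one line of derivation. If everyone was dosed weekly, the formula can stay as it is.

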## CONFIDENTIAL

DE Cohort	Screening a	Cycle (Induction Period)			Follow-Up (post-final dose administered)		
Study Procedure		Intervent (In-P	ion Period atient)	Observation Period (Outpatient)	TDV⁵	Follow- Up	Notes
Week	≤4	1	- 2	3 - 4	+4		
Day	≤28	-1	1 - 13	14 - 28	+30d		
							renal consult). TLS prophylaxis and fluids should be continued over each dosing cycle as clinically indicated. Refer to Section 6.4.1.2 for prophylaxis and management of TLS.
Efficacy Assessments							
BM Sample for Disease Assessment	Х		D40 (i.e.D12 of Cycle 2)	D84 (i.e. D28 of Cycle 3)	Х		BM aspirate and core biopsy samples are required at Screening, Day 12 of Cycle 2 (within EOI+24hr), and D28 of Cycle 3 (+2 days is allowed, but must be before Day 1 of next cycle). The collection time point is mandatory after the last cycle of intense dosing (i.e. D28 of Cycle 3) before moving into maintenance +2 days is allowed for BM sample collection at each time point provided it occurs before next treatment cycle starts. Both BM aspirate and core biopsy samples should be used for Disease Assessment and pharmacodynamics.
Pharmacokinetics (PK	), Pharmacod	ynamics, a	nd Genomi	cs		1	
BM Samples	Х		D40 (i.e.D12 of Cycle 2)	D84 (i.e. D28 of Cycle 3)			BM aspirate and core biopsy samples are required at Screening, Day 12 of Cycle 2 (within EOI+24hr), and Day 28 of Cycle 3 (+2 days is allowed, but must be before Day 1 of next cycle). Consult GSK Medical Monitor if bone marrow samples could not be obtained for any reason during these time points.

## CONFIDENTIAL

DE Cohort	Screening a	Cycle (Induction Period)			Follow-Up (post-final dose administered)		
Study Procedure		Intervention Period (In-Patient)		Observation Period (Outpatient)	TDV⁵	Follow- Up	Notes
Week	≤4	1	- 2	3 - 4	+4		
Day	≤28	-1	1 - 13	14 - 28	+30d		
							Alternative on-treatment biopsy timings may be explored, as discussed with GSK Medical Monitor. Additional unscheduled BM aspirate and/or biopsies may be performed any time during the treatment period upon participant consent for this optional procedure.
Progressive Disease BM Sample					Х		Although not required, BM aspirate and core biopsy at the time of disease progression is highly encouraged.
Whole blood (flow cytometry)			Х	Х	Х		Sample collection should occur on Days 1, 5, 9, 12, 13 and 28 of each cycle. On Days 1 and 9: predose, EOI+4h, EOI+8h, EOI+12h, and EOI+24h time points will be collected; On Day 5: predose and EOI+8h will be collected; On Day12: predose, EOI+8h, and EOI+24h time points will be collected; For Days 13 & 28: only one time point (any time) will be collected. Collection of samples at disease progression is optional.
Serum (cytokines)			Х	Х	Х		Sample collection should occur on Days 1, 5, 9, and 12 of each cycle. On Days 1 and 9: predose, EOI+4h, EOI+8h, EOI+12h, and EOI+24h time points will be collected;

## CONFIDENTIAL

DE Cohort	Screeningª	Cycle (Induction Period)			Follo (post-fir admini	w-Up nal dose stered)	
Study Procedure		Intervention Period (In-Patient)		Observation Period (Outpatient)	TDV⁵	Follow- Up	Notes
Week	≤4	1	- 2	3 - 4	+4		
Day	≤28	-1	1 - 13	14 - 28	+30d		
CC//2745417 algebra							On Day 5 and 12: predose and EOI+8h will be collected. Collection of serum samples at disease progression is optional.
PK			X				Cycle 1: PK sample collection times: Day 1 at predose (within 1h prior to dosing), EOI +5m, +15m, +30m, +45m, +1h, +2h, +4h, +6h, +8h, +12h and +24h; Day 4 at predose; Day 5 at predose and EOI+5m, +4h, +8h, +24h; Days 8 at predose (within 1h prior to dosing) and EOI+4h, EOI+8h, EOI+12h and EOI+24h; and Day 12 at predose (within 1h prior to dosing) and EOI+8h and EOI+24h. Cycle 2: PK sample collection times: Day 1 at predose (within 1h prior to dosing) and EOI +5m, +1h, +4h, +8h, +12h and +24h; Day 4 at predose; Day 5 at predose and EOI +5m, +4h, +8h, +24h and Days 8 and Day 12 at predose (within 1h prior to dosing) and EOI +8h Cycle 3: PK sample collection times: Days 1 and 5 at predose (within 1h prior to dosing) and EOI +5m, +1h, +4h, +8h, 12h and +24h; Day 4 at predose; and Days 8 and Day 12 at predose and EOI +5m, +1h, +4h, +8h, 12h and +24h; Day 4 at predose; and Days 8 and Day 12 at predose and EOI +5m, +1h, +4h, +8h, 12h and +24h; Day 4 at predose; and Days 8 and Day 12 at predose and EOI +5m, +1h, +4h, +8h, 12h and +24h; Day 4 at predose; and Days 8 and Day 12 at predose and EOI +5m, +1h, +4h, +8h, 12h and +24h; Day 4 at predose; and Days 8 and Day 12 at predose and EOI +5m, +4h, +8h, and +24h.

